EPI data: In Malawi, monthly data for each health facility, on routine vaccine delivery, extracted from the DVDMT system. They are migrating to DHIS2 and the facility level data will then be extracted from DHIS2 by the MVIP data manager. In Kenya, DHIS2 is being used for EPI data, RTS,S variables are being incorporated. Facility level data will be extracted by the MVIP data manager. In Ghana, DHIS2 is being used, access to these data is being requested.

AEFI and AESI: Mechanisms for access to data on AEFI and AESI in each country are being developed.

22. Data sharing plans

Although plans are not finalised it is envisaged that data sets be lodged with an appropriate data archiving service. We will ensure that the data lodged in the repository will be anonymised, fully documented, and in a format that can be reused by the widest audience, and in compliance with requirements of journals in which results are to be published.

The choice of public repository should be determined by WHO policy.

The terms under which data are shared will be developed using best practice of the WHO's archiving services.

Data sharing agreements, setting out the terms under which research data are to be shared, will be developed.

23. Costs and cost effectiveness

A costing analysis will be conducted as a sub-study within the broader evaluation of the feasibility of RTS,S/AS01 introduction. The costing study will evaluate the cost of introducing and delivering RTS,S/AS01 in each of the pilot countries (Ghana, Kenya, and Malawi) through the analysis of the cost of introduction (start-up cost) and delivery (recurrent cost) of RTS,S/AS01 and the generation of evidence on the cost implications of RTS,S/AS01 introduction and delivery. Understanding these costs will be critical in assessing economic feasibility of delivering RTS,S/AS01 as well as help inform decision making and planning around further use of the vaccine.

Specific objective for costing analysis: The costing study specifically aims to estimate the incremental cost of introducing and delivering RTS,S within the MVIP pilot areas through the routine immunization programs.

Approach: The analysis of costs will be done from the governments' perspective and will only include the incremental cost of introducing and delivering the RTS,S vaccine into the existing immunization programs in each of the three countries. The study will take an activity-based costing approach where all activities associated with the introduction and delivery of vaccine are identified and costed individually. Both financial and economic costs associated with be included in the analysis.

The costing analysis will gather and utilize actual data on activities, costs/expenditure, and coverage (administrative) data from the pilot introduction in three countries. Data on activities, costs, and outcomes will be gathered from health administrative units and facilities at all levels (national and sub-national) of the countries.

- At the National level, data collection will occur at the immunization program (EPI) and the central level vaccine store. Data on vaccine storage and supply chain costs will also be gathered from all regional level vaccine stores included in the MVIP (including Phase 4) areas.
- Data related to service delivery will be collected from a sample of health facilities. The sample frame will include all interventions clusters (districts in Ghana and Malawi; sub-counties in Kenya).
- Fifteen to twenty-five percent of clusters from the sample frame will be selected as sample clusters for data collection using stratified a random sampling method selected for each country. Stratification will be based on the following variables, as prioritized by the National level MVIP stakeholders:
 - Geography (urban/rural)
 - Population density (high/medium/low) [or expected number of doses delivered]
 - EPI performance (*e.g. high/medium/low*)
- The sampling frame will guide the selection of health facilities within each sample cluster for data collection according to facility type (for example - sub-health post, primary health care center, dispensary, if relevant), geography (urban/rural), ownership (private/public), and population served (low volume/high volume).
- Within each sample cluster, two public health facilities (ideally, two for each level type) will be purposively selected in consultation with the local health officials in country. Selection of health facilities will seek to capture variation in within cluster heterogeneity such as urban/rural differences, high/low volume facilities). At least one private sector facility will also be selected in each cluster.
- In the event country plans to deliver vaccine through community outreach and mop-up activities, data will be gathered from at least one such events in each sample sub-region.

To facilitate the costing analysis, an excel based Malaria Vaccine Introduction planning and Costing Tool (MVICT) has been developed to guide data gathering and generate cost estimates. The tool has been reviewed by WHO's Immunization and Vaccine Implementation Research Advisory Committee (IVIR-AC) and validated for each country through a preliminary analysis of the cost of continuing vaccination.

The costing analysis will only incorporate resources spent on introduction and delivery of RTS,S/AS01, excluding costs that are primarily incurred for the evaluation component of the MVPE. All MVIP related activities will be categorized as components of the immunization program, including micro-planning; training; vaccine procurement; development of information, education and

communication (IEC) and social mobilization materials; cold chain expansion; service delivery; supervision; and monitoring of vaccine delivery. Across all activities, both the value of financial and economic resources will be measured and will be further categorized as recurrent and capital costs. Table 1 shows a framework of costs of major activities for MVIP vaccination that would be categorized under recurrent or capital costs and financial or economic costs. Please note that collecting data on RTS,S/AS01 introduction activities is a part of the study data collection, and therefore the activities listed in the tables below may not be comprehensive.

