So for 90% coverage of anti-meningitis vaccine, and 1% coverage of RTSS, if all the RTSS-vaccinated received anti-meningitis vaccine, $F' = 0.81$ and $G' = 1$. If Rv^* is 10.5, and d is 1%, this gives R with contamination reduced by a factor of $1 / [0.01 \times 10.5 \times 0.81 + (1 - 0.01) \times 1] = 0.93$. If d is 2% this factor is 0.87 and 5%, 0.73. The values with no confounding are 0.91, 0.84, 0.68 for 1%, 2% and 5% contamination. So allowing for confounding in implementation areas, and contamination and confounding in comparator areas, if contamination is 1%, we would aim to exclude a target R value of $7.878 \times 0.93 = 7.3$, or for $d = 2\%$ or 5% , values of 6.8 or 5.7.

Effect of contamination on other outcomes (examples for cerebral malaria (R_v^* 2.57); mortality, 0.9, severe malaria, 0.7):

Power calculations:

Power was estimated using simulations in which the number of events in cluster j and age group k , was a random value from a poisson distribution with mean equal to $r \cdot k_{ij} y_{jkt} \theta_{jk}$, where r is the assumed underlying incidence rate, k_{ij} is an adjustment factor for the relative access to hospital i for cluster j (explained below), y_{jkt} is the person time in cluster j in age group k at time t , and θ_{jk} is the rate ratio for the outcome associated with vaccine introduction, for cluster j and age group k . $\theta_{jk} = \theta$ for vaccine-eligible age group in clusters in the intervention arm, $\theta_{jk} = 1$ otherwise. For each simulation, the ratio of the number of events between the two age groups was compared between arms using a ratio estimator. The simulation was repeated 10,000 times, to determine the distribution of the estimate of θ and of the 95% confidence limits. Simulations were done for null value ($\theta = 1$) for a range of assumed underlying incidence rates, and for various values of $\theta > 1$ (safety) and $\theta < 1$ (impact) to estimate power to detect or exclude effects of interest. Simulations were repeated for a range of values of the underlying incidence rate, for various time points, in order to determine the number of events that would be required to have adequate power, at each time point.

Relative access to hospital:

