(average for the period from vaccine introduction to Dec 2020), and estimates of the degree of contamination (% admissions (or % deaths) in vaccine-eligible age groups in comparator areas, who had received RTSS-1).

Country	Coverage of RTSS-1	Contamination (RTSS-1 coverage in comparator areas in hospital catchments)	
		from mortality surveillance (HBR or recall)	from hospital admissions (HBR or recall)
Malawi	72.3%	4.8%	2.7%
Ghana	69.0%	0.0%	5.9%
Kenya	79.8%	5.3%	4.6%
TOTAL	73.7%	3.4%	4.4%

Table 5: Power to detect or exclude effects on safety outcomes, of the magnitude observed in the phase 3 trial, and power to detect impact on hospital admission with severe malaria, and on all-cause mortality

	Effect in the phase3 trial ¹	Corresponding effect size, allowing for coverage ²	Effect size allowing for contamination ³	Effect size allowing for confounding ⁴	Number of events required for given power to detect or exclude effects of the given size ⁵	
					90% power	80% power
Safety outcomes:						
Meningitis	10.5	8.00	5.80	5.66	90	70
Cerebral malaria	2.57	2.16	2.03		400	300
Gender interaction (mortality)	1.7	1.52	1.47		2000	1500
Impact:						
Severe malaria ⁶	0.66	0.75	0.76		4000	3000
Mortality ⁷ a)	0.898	0.92	0.93		24000	18000
b)	0.864	0.90	0.90		17600	13100

1 In the phase 3 trial, the observed rate ratio for meningitis (RTS,S/AS01:control) was 10.5, and for cerebral malaria, 2.57. Among girls, there was a higher mortality rate in RTS,S/AS01 recipients than controls, the mortality ratio was 2 over the whole trial period, and was 1.7 in the first part of the trial (from enrolment until the 4th dose was administered) and 3.4 in the latter part of the trial.

2 Assuming coverage of RTSS-1 of 74% (the average value in Table 4)

3 Assuming coverage of RTSS-1 in comparator areas is 4%

4 Confounding: For meningitis, assuming RTSS-recipients more likely to have received other vaccines that would prevent meningitis (90% coverage of anti-meningitis vaccines, 50% efficacy against all-cause meningitis, all RTSS recipients have received anti-meningitis vaccine). Based on preliminary data from baseline surveys, EPI coverage did not appear to differ between high and low malaria prevalence areas, and was similar in children who tested positive for malaria infection by RDT and children who tested negative. We have therefore assumed no confounding for impact outcomes.

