- % children who received RTS,S4 who had previously received less than 3 doses of RTS,S.

18. Other interventions that might affect MVPE outcomes

A diary of other interventions (e.g. LLIN distribution, IRS campaigns, azithromycin MDA, expansion of community case management, creation of new health facilities) maintained for each cluster would allow reporting of contextual information about the possible influence of other interventions taking place in study clusters during the MVIP. These are being recorded by the evaluation partners and reported to WHO as part of quarterly technical reports. Likewise, the PATH and WHO MVIP team members in each pilot country records similar events that can affect EPI delivery of the RTS,S vaccine.

19. Calculation of rate ratios and rate differences

Incidence of the primary safety outcomes (probable meningitis, confirmed meningitis, cerebral malaria) and impact outcomes (deaths, deaths excluding injuries, and severe malaria) will be compared between comparator and RTS,S areas, in each country and for the three countries combined. For mortality, the evaluation is powered to estimate effects within each country by the end of the 46 months. For meningitis, primary analysis will be pooled across the three countries.

Rate ratios and rate differences, with 95% and 99% confidence intervals, will be calculated as in the table below. Secondary safety and impact outcomes listed in Table 5 will be analysed in the same way.

Table 8: Dummy table for effect measures for safety and impact outcomes

Outcome	Analysis populations* primary (secondary)	Comparator N/PYAR rate	RTS,S N/PYAR rate	Rate ratio (95%CI)	Rate difference (95%CI)
Safety:					
Probable meningitis	A1 (A4)				
Confirmed meningitis	A1 (A4)				
Cerebral malaria	A1 (A4)				
Impact:					
Deaths	A2 (A4)				
Deaths (excl. injury)	A2 (A4)				
Severe malaria	A2 (A4)				

*A1: eligible for RTS,S; A2: eligible for 3 doses of RTS,S; A4: received 3 doses of pentavalent vaccine

(Note: For severe malaria, if a reduction in the number of admissions for all-cause febrile illness is observed that is commensurate with the reduction in severe malaria, this would give reassurance that the reduction in severe malaria was not caused simply by a reduction in the prevalence of parasitaemia without prevention of severe illness.)

Subgroup analyses

Gender

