(We could have calculated the ratios within each cluster and then compared the mean or geometric mean between the two arms, this would give equal weight to each cluster (and there would need to be an adjustment to allow for clusters with zero events in group B). The approach we will use for the MVPE weights clusters according to their population).

The variance of R_j is [23,22]:

$$V(R_j) = \left(\frac{m_j}{(m_j-1)n_{j,B}^2} \right) \sum_{i=1}^{m_j} (n_{j,i,A} - R_j n_{j,i,B})^2 \quad j = 0,1$$

where m_j is the number of clusters in arm j , R_j is the point estimate of the rate ratio in area j , and $n_{j,i,A}$ and $n_{j,i,B}$ is the number of events in group A in cluster i in area j and $n_{j,i,B}$ is the number of events in group B in cluster i in area j , and $n_{j,B}$ the total events in group B in area j .

The log rate ratio comparing the RTS,S and comparator areas is

$$D = \log(R_1) - \log(R_0), \text{ with variance } V(D) = V(R_1)/R_1^2 + V(R_0)/R_0^2.$$

We will have an estimate of D for each country, D_1 , D_2 and D_3 , the combined estimate is then

$$D_{\text{combined}} = \sum D_i / V(D_i) / \sum 1/V(D_i), \quad i=1..3, \text{ and the variance is } V(D_{\text{combined}}) = 1 / \sum [1/V(D_i)].$$

To test for interaction by country (Cochran's Q test), $\sum [(D_{\text{combined}} - D_i)/V(D_i)]^2$ is referred to the X^2 distribution with 2 degrees of freedom [24].

The final rate ratio is given by $\exp(D_{\text{combined}})$ and the $100(1-\alpha)\%$ confidence interval by

$$\exp[D_{\text{combined}} \pm t_{\alpha/2, C-6} \sqrt{V(D_{\text{combined}})}], \text{ with df equal to the total number of clusters } C \text{ less } 2 \times 3 = 6.$$

This final stratified rate ratio represents *the average increase or decrease in incidence of the outcome due to introduction of RTS,S vaccine, in the age group of children eligible to receive the vaccine, across all three countries*. As for the rate differences, the estimated value will depend on the analysis population chosen (A1, eligible for RTS,S; A2 eligible for 3 doses of RTS,S; or A3 eligible for 3 doses and followed up to 39 months of age) and the time point when analysis is done.

It is not planned to adjust for cluster-level covariates. (The baseline surveys are not designed to produce accurate estimates of malaria transmission and other indicators for individual clusters). We will adjust analyses of impact for transmission strata, in a secondary analysis.

Gender interaction

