Annex 3: Summary of outcomes and analysis methods

[figure not shown]
Objectives	Outcomes	Methods	Timing	Analysis population
Impact: effect of RTS,S introduction on:				
All-cause mortality	Mortality (excluding injury)	Rate ratio and rate difference	When intermediate analysis is done (driven by accrual of safety outcomes), and at 46 months	A2
Severe malaria	Hospital admission with severe malaria	Rate ratio and rate difference (cases in hospital catchments)		A2
Secondary outcomes	Severe malaria anaemia; transfusions; all-cause admissions; malaria admissions; non-malaria admissions	Rate ratio and rate difference (cases in hospital catchments)		A2
Safety: effect of RTS,S introduction on rate of admission with:				
Meningitis	Hospital admission with probable meningitis	Rate ratio and rate difference (cases in hospital catchments)	When 80-100 cases have accrued in total in the 1-59 age group	A1
Cerebral malaria	Hospital admission with cerebral malaria	Rate ratio and rate difference (cases in hospital catchments)	to be defined	A1
Evidence of differential effect on mortality by gender	Mortality (all causes excluding injury)	Interaction by gender (comparison of proportion	When about 2000-2500 deaths (excluding injury) have accrued, among vaccine-eligible age groups	A1

boys and girls vaccinated,
among deaths in vaccine-
eligible age groups in RTS,S
clusters)

[figure not shown]
Objectives	Outcomes	Methods	Timing
Feasibility:			
Uptake of 3 doses by 12 mnths of age	Coverage of RTS,S doses 1,2,3	Ratio estimator (survey weighted); Kaplan Meier	When midline survey has been completed
Uptake of 4 doses by 27 mnths of age	Coverage of RTS,S doses 1,2,3,4	Ratio estimator (survey weighted); Kaplan Meier	When endline survey has been completed
Impact of RTS,S on EPI uptake	Coverage of penta-3 etc	Ratio estimator (survey weighted); Kaplan Meier	When midline survey has been completed
EPI data:			
Coverage of dose 4	Number of doses administered, by antigen and dose number	Descriptive	When intermediate analyses are done, and at month 46
Impact of RTS,S on EPI delivery	Number of doses administered, by antigen and dose number	Comparison of rates and drop-off rates between areas	

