For meningitis, the 10-fold increase in risk in vaccinated children observed in the phase 3 trial, would correspond to a rate ratio of about 5 to 6 after allowing for expected levels of coverage and contamination. The minimum number of cases required for 90% power to detect an increase in incidence due to RTS,S introduction, if the true rate ratio is 5, is about 80 to 100 cases in the vaccine-eligible and non-eligible age groups combined, Figure A4.5. (The number of events needed, is not the same at each time point, because the power depends on the relative number of cases in vaccine-eligible and non-eligible age groups and is optimal when these are equal).

Figure A4.5. Number of meningitis cases required for 90% power to detect a 5-fold increase in incidence due to RTS,S introduction, for analyses at different timepoints.

[figure not shown]
[figure not shown]

Figure A4.6. Number of meningitis or cerebral malaria cases required for 90% power to detect a 2- to 5-fold increase in incidence due to RTS,S introduction (for an analysis at the end of the evaluation).

In the phase 3 trial, among girls, mortality was 2-fold higher in those who received RTS,S/AS01 than in those who received the control vaccine (risk ratio 2.0), while among boys, mortality was lower in those who received RTS,S/AS01 (risk ratio 0.76), giving a ratio of mortality ratios of 2.62. This gender difference appeared stronger in the latter part of the trial, when, among girls, mortality was 3.4-times higher in RTS,S recipients than controls, while in boys mortality was slightly lower (risk ratio 0.88), giving a ratio of mortality ratios of 3.84.

Mortality ratios in the phase 3 trial

	Whole period	0-20mths	21+mths
Mortality risk ratio girls:boys, RTS,S group	1.50	1.75	1.12
Mortality risk ratio girls:boys, control group	0.57	0.72	0.29
Ratio RTS,S:control	2.62	2.43	3.84
Ratio of mortality risk RTS,S:control, in girls	2.00	1.70	3.40
Ratio of mortality risk RTS,S:control, in boys	0.76	0.70	0.88
Ratio girls:boys	2.62	2.43	3.84

(These risk ratios are approximately equal to mortality rate ratios)

If RTS,S/AS01 coverage in the MVPE is 60% in both boys and girls, a ratio of mortality ratios of 2.6 translates to a ratio, at population level, of 1.9. A ratio of 2.0 among RTS,S recipients would translate to a ratio of 1.6, and a ratio of 1.5 to a ratio of 1.3.

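### The 80-100 meningitis case target appears to be calculated for one unstratified ratio estimator, but the primary analysis pools three sparse country estimates and has no rule for empty cells

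*SAP*

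**What the plan says.** **Power.** SAP section 8 (Power calculations) draws Poisson counts by cluster and age group and says: "For each simulation, the ratio of the number of events between the two age groups was compared between arms using a ratio estimator". The runs gave the distribution of the estimate and its 95% limits. Country strata and weights are not mentioned.

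**Target and trigger.** Annex 4 states that the number needed for 90% power at a true rate ratio of 5 "is about 80 to 100 cases in the vaccine-eligible and non-eligible age groups combined". Annex 3 times the meningitis analysis accordingly: "When 80-100 cases have accrued in total in the 1-59 age group". Table 5 lists the phase 3 effect, its successive dilutions to 5.66, and then the events for 90% and 80% power: "Meningitis 10.5 8.00 5.80 5.66 90 70".

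**Analysis.** SAP section 19 says: "For meningitis, primary analysis will be pooled across the three countries". Section 20 (Rate ratios) defines the pooling: "We will have an estimate of D for each country". These estimates are combined with weights 1/V(D), and the t distribution has C-6 degrees of freedom, which is 71 for the 77 catchment clusters. An adjustment for zero events is mentioned only for the per-cluster ratio method that section 20 sets aside. The Stata code in Annex 2 handles one set of clusters. It contains neither the country-combination step nor a rule for empty cells.

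**The concern.** Summing events over all clusters before taking a ratio is not the same estimator as taking three country ratios and weighting them. With frequent events the difference is negligible. With 80-100 cases and a 5-fold effect, the comparator vaccine-eligible cell holds only about two or three cases per country.

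Two things follow. A country whose comparator eligible count happens to be low gives a high ratio with a large variance, so it gets little weight and the pooled value moves toward 1. If that count is zero, the country's log ratio is undefined and the plan does not say what to do.

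Meningitis is a primary safety outcome. Its analysis is triggered by this case count, and SAP section 1 envisages that a recommendation on wider use might follow before the final data.

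**Working it through.** **1. Expected counts.** Take equal arms and let r be the eligible to non-eligible event ratio with no effect. The eligibility rules and start dates give r of about 0.29 at month 24. With u non-eligible cases per arm and a rate ratio of 5, the total is N = u(2 + 6r).
- N = 80: u = 80/3.74 = 21.4; comparator eligible 0.29 × 21.4 = 6.2; RTS,S eligible 31.0.
- N = 100: u = 26.7; comparator eligible 7.8; RTS,S eligible 38.8.

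**2. The plan's figure, by delta method.** Var(log ratio) = 1/(ru) + 1/(5ru) + 2/u.
- N = 80: 0.161 + 0.032 + 0.094 = 0.287; power = Φ(1.609/0.536 − 1.96) = 85%.
- N = 90 gives 89% and N = 100 gives 92%.

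A single unstratified estimator therefore reproduces 90% power within 80-100 cases.

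**3. Which estimator the plan simulated.** The Annex 4.2 table gives the smallest excludable ratio with 80%/90% power at 0.02/1000 (taken as per child-year). It was re-simulated without the access factors.

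| Month | SAP | Single | Pooled by country |
|---|---|---|---|
| 18 | 10.5/18.3 | 10.5/18.1 | 15.0/26.0 |
| 24 | 5.8/8.2 | 5.9/8.2 | 6.7/9.7 |
| 36 | 3.4/4.2 | 3.4/4.2 | 3.5/4.3 |

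With the access factors included, the single estimator matches only if the rate is raised to 0.03/1000 (10.8/18.7, 5.9/8.4, 3.5/4.3). Pooling by country at that rate again misses at months 18 and 24.

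**4. Empty cells.** With equal thirds, the comparator eligible mean per country is 6.2/3 = 2.07 at 80 cases, so P(zero) = exp(−2.07) = 0.126 and P(at least one of three) = 1 − 0.874³ = 33%. At 100 cases the mean is 2.58 and the result is 21%. Over all simulated settings, about 10-58% of runs at 80-100 cases had a country that could not be estimated.

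**5. Why the weights pull toward 1.** Take two countries at the 80-case averages (RTS,S eligible 10.3, non-eligible 7.1 per arm), one with 1 and one with 4 comparator eligible cases. Their ratios are 10.3 and 2.6. Their variances are 0.097 + 0.140 + 0.140 + 1 = 1.38 and 0.097 + 0.140 + 0.140 + 0.25 = 0.63. The country pointing to greater harm gets 0.63/1.38 = 0.46 of the other's weight.

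**6. Simulated power, rate ratio 5.** Inputs: 77 catchment clusters (32 Ghana, 28 Kenya, 17 Malawi), cluster sizes from SAP Table 1, Poisson counts and two-sided 95% intervals. Assumed, because the documents give no case split: eligible share with no effect 0.2-0.4, or from the eligibility rules at months 24 and 46; and country shares of cases by births, equal, or 60/20/20. The shares by births are 32 × 4628 : 28 × 5559 : 17 × 5115, or about 38:40:22.

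| Estimator | 80 | 90 | 100 cases |
|---|---|---|---|
| Single ratio | 85-89% | 89-92% | 92-94% |
| Section 20, 0.5 added to empty cells | 80-86% | 85-90% | 89-93% |
| Section 20, country dropped | 70-81% | 78-87% | 85-91% |
| Country-stratified Mantel-Haenszel | 85-88% | 89-91% | 92-94% |

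With month-46 person-time the single estimator gives 82/87/90%, and section 20 gives 80/85/89% (0.5 added) or 75/82/87% (dropped). The median section 20 estimate for a true 5 is about 4.7-5.1 (0.5 added) or 4.2-5.0 (dropped). Section 20 reaches 90% power at about 100-105 cases with 0.5 added and about 110 if countries are dropped.

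**7. Table 5, rate ratio 5.66.** With 0.5 added, 90 cases give about 88-93% and 70 cases about 80-84%, against the stated 90% and 80%. With countries dropped, they give about 82-89% and 64-76%.

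**The case against.** The SAP never says that its simulation ignored country. The country estimates in section 20 are ratio estimators too, and the match to Annex 4.2 needs either no access adjustment or a higher rate than stated. This stands as a caveat: the mismatch is an inference, though a well-supported one.

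A reader might infer that true power is about 70% and that Table 5 is wrong. The documents do not support that. The low figures require dropping a country with an empty cell, a rule the SAP does not contain. With a 0.5 correction Table 5 roughly holds. Part of the gap at 80 cases also comes from the low end of a rounded range, since the single estimator misses 90% there as well.

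Nor should one infer that the evaluation cannot rule out a 5-fold increase, or that a real one would go unnoticed. The SAP aims to detect or exclude, and exclusion power with no true effect falls by only about 1-4 points. The DSMB sees data every six months, apparent excesses lead to further analyses, and the final analysis is at month 46. By 150 cases the estimators differ by about 2 points at most.

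**Conclusion.** The point holds as a mismatch between the power calculation and the primary analysis, together with a missing rule for empty country-arm cells. At 90 cases the chance of missing a true 5-fold increase is about 10-15% with a 0.5 correction and 13-22% if countries are dropped, against the 10% planned. With the correction, the loss relative to a single estimator is about 3-6 points at month 24 and 1-2 points at month 46. It therefore matters most at the event-triggered intermediate analysis.

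Without a stated rule, a choice worth up to about 10 points of power would be made after the data are seen. The figures rest on assumed case splits, country shares and spread of cluster size and access. The point does not extend to the more frequent outcomes: at 400 cerebral malaria cases the two estimators gave the same power.

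**What to change.** Preferred: for meningitis, pre-specify a country-stratified ratio that tolerates empty cells. A Mantel-Haenszel form is Σ(n1A·n0B/N) ÷ Σ(n0A·n1B/N), summed over countries, where N is the country's total events and the variance comes from between-cluster variation within each country-arm. It keeps the strata and uses every country. In simulation its type I error was about 4-6% and its median 5.1-5.3 for a true 5. One alternative coding gave slightly lower power (81-85/87-90/90-93%), so the variance formula should be written into the SAP and the simulation rerun with it. Set the trigger at 90-100 cases.

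Alternative: keep section 20, state the zero-cell rule, rerun the power simulation with that exact estimator, and restate either the power at 80-100 cases or the trigger (about 100-110 cases for 90%).

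The cost is SAP wording and a few lines of code. The downside is a different pooling formula for meningitis than for other outcomes or, under the alternative, a slightly later analysis.
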